9.5 Other Centralized Study Procedures

9.5.1 *Clinical laboratory parameters*

A central laboratory will be used for all scheduled laboratory tests in this study except for the pregnancy test which will be done locally and eGFR which will be assessed locally (for screening) and centrally (for safety evaluation). The investigator will be provided with a list of normal ranges prior to the start of the study. The central laboratory will provide the necessary kits to collect the blood samples and will also provide appropriate information regarding shipping of the samples.

Care should be taken during blood sampling in order to avoid potential generation of false positive blood value (e.g., by inappropriate use of the tourniquet or forceful withdrawal of blood). Each original laboratory report will be filled with the subject's source document.

All laboratory reports must be promptly reviewed by the Investigator, and upon review, initialed and dated by the Investigator. Change(s) in post-dose test values considered clinically significant, which would require either additional control or therapy, must be documented in the subject's source document and, in case of disturbing or influencing factor(s) on values/samples, details of the appropriate value(s) and the source of disturbance or influence (e.g. quality of sample, co-treatment etc.) are to be recorded. All values considered clinically significant will be reported as AEs or alternatively according to investigator's judgement as medical history if measured at baseline and related to an underlying disease.

Laboratory samples obtained for this study will be used only for this study. Samples obtained in this study will not be retained or used for any other purposes.

 CONFIDENTIAL	Protocol No. GDX-44-008 Version No.4.0 including amendments 1 and 2 12 December 2017	Page 42 / 64
---	--	--------------

10. SAFETY REPORTING

10.1 Adverse Event

10.1.1 *Definition of Adverse Event*

An Adverse Event (AE) is any untoward medical occurrence in a patient or investigation subject administered a pharmaceutical product and which does not necessarily have to have a causal relationship with this treatment.

An adverse event can therefore be any unfavorable and unintended sign (including an abnormal laboratory finding, for example), symptom, or disease temporally associated with the use of a medicinal product, whether or not considered related to the medicinal product.

Any disease identified and diagnosed by study contrast-enhanced MRI will not be considered as AE.

10.1.2 *Recording/Collection of Adverse Events*

The Investigator or his/her designee will invite the subject to report any abnormality experienced as part of the usual clinical follow-up.

All adverse events, whether considered as related or not to the Investigational Medicinal Product and/or the imaging procedure should be reported in the medical file and the CRF and followed up from onset to resolution or stabilization of sequelae. If no follow-up is performed, the investigator must provide a justification.

In order to ensure complete safety data collection, all adverse events occurring from ICF signature until Day+1, must be reported and followed even if no IMP was administered. The investigator shall document all adverse events in the medical file and the appropriate section of the CRF.

In addition, if occurring after the safety visit at Day+1, events that the investigator thinks may be associated with the study medication/procedure must be reported to the sponsor at the optional Visit 4 and further regardless of the time between the event and the end of the study.

Safety information to be collected by the investigator with the same procedure as adverse events: medication errors and uses outside what is foreseen in the protocol, including misuse and abuse of the product, suspicion of transmission of an infectious agent via an IMP, unusual failure in efficacy, overdose (symptomatic or not), all reports of pregnant or breastfeeding women exposure even if uneventful, all reports of suspected drug-drug interaction with another product (symptomatic or not).

In this protocol, the overdose is defined as more than 0.3 mmol/kg for P03277. Any overdose, with or without adverse event, will be reported as AE and, in addition, on SAE form if the associated event is serious.

10.1.3 *Description of Adverse Events*

The following guidelines and definitions should be used by the investigator for the description of an AE when reporting information:

- **Nature of AE:** preferably an overall diagnosis or syndrome, rather than individual symptoms or signs. The investigator must report AE using standard medical terminology. The same terms should be used in the source documentation and in the CRF.
- **Date and time of onset:** date and clock time of the AE start
- **Intensity:**
 - Mild: the subject is aware of the sign or symptom, but it does not interfere with her/his usual daily activities and/or it is of no clinical consequence

 CONFIDENTIAL	Protocol No. GDX-44-008 Version No.4.0 including amendments 1 and 2 12 December 2017	Page 43 / 64
---	--	--------------

- Moderate: the AE interferes with the usual daily activities of the subject or it is of some clinical consequence
 - Severe: the subject is unable to work normally or to carry out his/her usual daily activities, and/or AE is of definite clinical consequence.
- **Date of the event end** (or consolidation): The real date of event end will be entered if the event has come to its end on the date of end of subject's follow-up. If the AE is still ongoing by the time of end of study follow-up for the subject (i.e. last study visit), the subject should be followed-up until AE resolution or a justification should be provided by the Investigator (i.e. chronic disease) in the medical file.
- **Causal relationship to the Investigational Medicinal Product:**
 - Related: the definition of adverse reaction implies a reasonable possibility of a causal relationship between the event and the IMP. This means that there are facts (evidence) or arguments to suggest a causal relationship.
 - Not related: Applicable when no IMP has been administered (pre-administration period) or when no causal relationship exists between the study drug and the event, but an obvious alternative cause exists (e.g. the subject's underlying medical condition or concomitant therapy).
- **Causal relationship to a study procedure – apart from IMP:**
 - Related
 - Not related
- **Outcome:**
 - Recovered/Resolved: the AE is no longer present at any intensity.
 - Recovered/Resolved with sequelae: the AE is resolved but residual effects are still present.
 - Not recovered/Not Resolved: the AE is still present at the last contact with the subject.
 - Fatal: this AE caused or directly contributed to subject's death.
- **Action taken with regard to administration of the IMP:**
 - No Action: for AE occurring during the pre-treatment/procedure or post-treatment/procedure period, or if the Investigational Medicinal Product dosing/administration remained the same in spite of AE being present.
 - Action taken :
 - No action
 - IMP withdrawn
- **Other action taken:**
 - AE-targeted medication: the subject took a medication (either prescription or non-prescription) specifically for this AE. The drug(s) should be reported in the appropriate section of the CRF ("concomitant drug" section until V3).
 - Other AE-targeted action: subject used other therapeutic measures (e.g. ice, heating pad, brace, cast...) or subject underwent a procedure (physiotherapy, additional laboratory test...) for this AE. The therapeutic measure(s) should be reported in the appropriate section of the CRF ("Action other than drug administered for the AE" section)
- **Assessment of the seriousness of the AE:** see [Section 10.2](#) for SAE definition.

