10.2 Serious Adverse Event

10.2.1 *Definition of Serious Adverse Event*

A Serious Adverse Event (SAE) is any untoward medical occurrence that at any dose:

 CONFIDENTIAL	Protocol No. GDX-44-008 Version No.4.0 including amendments 1 and 2 12 December 2017	Page 44 / 64
---	--	--------------

- Results in death
- Is life-threatening
- Requires hospitalization or prolongation of existing in subject's hospitalization
- Results in persistent or significant disability or incapacity
- Is a congenital anomaly or birth defect
- Is medically important: adverse events that are not immediately life-threatening or do not result in death or hospitalization but may jeopardize the subject or may require intervention to prevent one of the other outcomes listed in the definition above, should also be considered serious.

Life-threatening in the definition of a serious adverse event refers to an event in which the subject was at risk of death at the time of event; it does not refer to an event which hypothetically might have caused death if it were more severe.

Medical judgment should be exercised in deciding whether an adverse event/reaction is serious in other situations. In case of a SAE, the investigator is responsible for the measures to be taken to ensure the safety of the study participants.

The following safety issues qualify for immediate reporting to Guerbet since they may alter the current benefit-risk assessment of an investigational medicinal product, or would be sufficient to consider changes in the study drug administration or in the overall conduct of the study:

- Any post-study serious and/or unexpected adverse event that occurs after the subject has completed the study and that is considered as related to the Investigational Medicinal Product by the investigator (causality not excluded).
- Any new event likely to affect the safety of the subjects and that may be related to the conduct of the study or the development of the study drug such as:
 - A SAE which could be associated with the study procedures and which could modify the conduct of the study
 - A significant hazard such as an unusual failure in efficacy.
 - A new finding from a newly completed animal study.

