12.4 Safety Data

Safety analysis will be done using the safety set presented by dose and overall.

Extent of exposure

Duration between IMP administration and end of study, volume theoretically administered, volume actually administered, actual rate of administration, theoretical rate of administration will be tabulated.

 CONFIDENTIAL	Protocol No. GDX-44-008 Version No.4.0 including amendments 1 and 2 12 December 2017	Page 52 / 64
---	--	--------------

Frequency tabulation of theoretical volume actually administered and theoretical rate of administration actually performed will be also displayed.

Adverse events

All analyses of AEs will be based on the number of subjects with AEs. Adverse events occurring after D+1 that the investigators considers as related to P03277 /study procedures will be included in this analysis.

Adverse events will be coded with the most recent version of MedDRA at the time of the database lock.

The time period for the assessment of AEs will be divided into 3 mutually exclusive and exhaustive periods: before administration of P03277, after administration of P03277 until day +1 FU and after safety follow-up until biopsy if it is done.

Events will be classified as treatment-emergent (TEAE) if they started or increased after P03277 administration. This will also include events with missing intensity.

Partial start dates/times will be queried. If information is not available to reliably allocate to a session and period, the allocation will be agreed at the data review meeting before database lock. If there is any doubt about treatment emergence, AEs will be classified as treatment emergent.

In all summaries, recurring AEs (AEs classified with the same preferred term) for a given subject in a given period will be counted as a single AE. If severity is summarized, this will be the maximum severity.

Overall overview

The number (%) of subjects having at least one Treatment Emergent AE (TEAE) as follows will be summarized for:

At least one TEAE

At least one adverse reaction (relationship to study treatment classified as 'Related')

At least one TEAE with action taken with study treatment

At least one TEAE with classifications of outcome

The table will show the same information for serious AE, defined as AEs with serious classified as 'yes' or missing.

The table will be repeated for all AEs

Distribution of AEs and SAEs

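### The two causality categories do not cover every post-injection event, and an event with missing causality is left out of the adverse reaction count

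*Protocol*

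**What the plan says.** Section 10.1.3 tells the investigator how to describe each adverse event and offers two answers for the causal link to the product. For *Related*, "the definition of adverse reaction implies a reasonable possibility of a causal relationship between the event and the IMP"; the next sentence explains: "This means that there are facts (evidence) or arguments to suggest a causal relationship". *Not related* covers events before administration and, after it, the situation "when no causal relationship exists between the study drug and the event, but an obvious alternative cause exists". There is no third answer.

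The same judgement is worded differently elsewhere. Section 10.2.1 lists, among issues for immediate reporting, post-study events that are "considered as related to the Investigational Medicinal Product by the investigator (causality not excluded". Section 10.1.2 says that after Day +1 "events that the investigator thinks may be associated with the study medication/procedure must be reported to the sponsor". Sections 7.2.2 and 12.4 refer to late events that the investigator considers related.

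Section 12.4 sets the count in the overview table: "At least one adverse reaction (relationship to study treatment classified as 'Related". For other uncertain or missing items that section leans the cautious way. Serious events are "defined as AEs with serious classified as 'yes' or missing". On treatment-emergent events it adds "This will also include events with missing intensity", and doubt about emergence is settled in favour of treatment emergence. Section 12.5 rules out imputation.

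**The concern.** A two-way classification works only if every event belongs to one side. Here one kind of event belongs to neither: it follows the injection, nothing positive points to the drug, and no other cause is obvious. Such events are plausible in subjects with chronic liver disease given one dose of a new agent. Investigators have to resolve the gap themselves and may do so differently.

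The adverse reaction count rests directly on that answer. It is part of the safety profile, a secondary objective, and is shown by dose, with one cohort of only 10 subjects. The counting rule is also out of step with its neighbours, since causality is the one item among these for which section 12.4 gives no cautious rule when the answer is missing. After Day +1 the judgement also decides whether an event is collected at all.

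**Working it through.** The protocol states no figure on this point, so there is nothing to reproduce. The check is one of logic, with simple arithmetic for scale.

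**Step 1: do the two categories cover every post-injection event?** Cross the two conditions used in section 10.1.3.

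| Facts or arguments for the drug | Obvious alternative cause | Category under 10.1.3 |
|---|---|---|
| yes | no | *Related* |
| yes | yes | *Related* (*Not related* also requires that there be no causal link) |
| no | yes | *Not related* |
| no | no | neither |

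The last row is the gap. *Related* fails for want of facts or arguments; *Not related* fails for want of an obvious alternative cause.

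**Step 2: what do the other wordings do with the last row?** Under the parenthesis in 10.2.1 the event would qualify, because causality has not been excluded. Under 10.1.2 it could qualify, because an association that may exist is enough. Under 7.2.2 and 12.4 it depends on what the investigator takes related to mean, which leads back to 10.1.3.

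**Step 3: how does section 12.4 count it?**

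| Item missing or in doubt | Treatment in 12.4 |
|---|---|
| Seriousness missing | counted as serious |
| Intensity missing | included as treatment emergent |
| Emergence in doubt | counted as treatment emergent |
| Causality missing | not counted as a reaction |

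The last line follows from the definition, which admits only events classified *Related*, together with the bar on imputation in 12.5.

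**Step 4: size per affected subject.** The inputs are the planned cohort sizes in section 8 (30 and 10, total 40) and subject-level counting in 12.4. The shift is 1/n:

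- n = 10: 1/10 = 10 points
- n = 30: 1/30 = 3.3 points
- n = 40: 1/40 = 2.5 points

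To show the effect on precision, assume no reaction is otherwise recorded and one affected subject is added. The protocol gives no count, so this is an illustration only. The exact (Clopper-Pearson) 95% upper limit is 1 − 0.025^(1/n) for zero events, and the 97.5th percentile of a Beta(2, n − 1) distribution for one event:

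| n | Rate, 0 to 1 subject | Upper limit, 0 to 1 subject |
|---|---|---|
| 10 | 0% to 10.0% | 30.8% to 44.5% |
| 30 | 0% to 3.3% | 11.6% to 17.2% |
| 40 | 0% to 2.5% | 8.8% to 13.2% |

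**The case against.** A reader might infer that the reaction rate is biased downward. The documents do not support that for unclear events. After injection *Not related* is the narrower box, because it demands an obvious alternative cause. An investigator who cannot name one and must choose may well tick *Related*, for which an argument is enough. That would bring unclear events into the count. This objection stands, and it removes any claim about direction except for blanks.

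A reader might also take section 10.2.1 as a competing classification. It is not one. The parenthesis belongs to a rule on immediate reporting of post-study events, and for events recorded on study only 10.1.3 defines the two answers. What remains is that one word carries different thresholds in different sections.

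Nor is the issue after Day +1 confined to non-serious events. Section 10.2.2 ends general reporting of serious events at Day +1 and then applies a single later threshold to events whether serious or not.

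Blanks may be rare. Section 10.2.2 makes causality mandatory on serious event reports, and section 15.3.1 obliges investigators to answer data queries. Section 12 is only a summary, and the statistical analysis plan, not shown here, may deal with missing causality. That is fair as far as it goes. But the protocol itself limits the count to *Related* while giving missing-value rules for the neighbouring items, and an analysis plan cannot fully repair judgements already recorded under incomplete definitions, or recover late events never collected.

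Finally, an unclear event up to Day +1 still appears in the treatment-emergent tables. This is correct and limits what is at stake.

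**Conclusion.** The point holds as a minor one. The two categories in 10.1.3 are not exhaustive, the threshold is worded differently in other sections, and 12.4 omits missing causality from the reaction count, against the cautious rules beside it. Unclear events may be classified inconsistently, and the protocol does not determine in which direction. Only for missing causality does the rule work one way: it can only lower the count, and this mainly concerns non-serious events.

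Each affected subject moves the reaction rate by 10 points (n = 10), 3.3 points (n = 30) or 2.5 points (n = 40). This assumes that the safety set matches the planned sizes and that the subject has no other event already counted as a reaction. How many subjects would be affected is unknown, and nothing in the protocol supports a guess. No test is planned, so no formal inference is at risk. What is affected is the consistency of one descriptive safety result and, after Day +1, of what is collected.

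**What to change.** - **Section 10.1.3:** state that *Not related* applies only before administration or when an obvious alternative cause exists, and that every other event is *Related*.
- **Section 10.2.1 and the texts on events after Day +1 (7.2.2, 10.1.2, 10.2.2, 12.4):** use the same wording, for serious and non-serious events alike.
- **Section 12.4:** define an adverse reaction as an event whose relationship is *Related* or missing, in line with the rule for seriousness. This is a counting rule like the existing one, so section 12.5 can stand.

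The cost is a few sentences in the protocol and matching CRF completion guidance. The downside is that the reported adverse reaction rate may rise slightly.

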10.2 Serious Adverse Event

10.2.1 *Definition of Serious Adverse Event*

A Serious Adverse Event (SAE) is any untoward medical occurrence that at any dose:

 CONFIDENTIAL	Protocol No. GDX-44-008 Version No.4.0 including amendments 1 and 2 12 December 2017	Page 44 / 64
---	--	--------------

- Results in death
- Is life-threatening
- Requires hospitalization or prolongation of existing in subject's hospitalization
- Results in persistent or significant disability or incapacity
- Is a congenital anomaly or birth defect
- Is medically important: adverse events that are not immediately life-threatening or do not result in death or hospitalization but may jeopardize the subject or may require intervention to prevent one of the other outcomes listed in the definition above, should also be considered serious.

Life-threatening in the definition of a serious adverse event refers to an event in which the subject was at risk of death at the time of event; it does not refer to an event which hypothetically might have caused death if it were more severe.

Medical judgment should be exercised in deciding whether an adverse event/reaction is serious in other situations. In case of a SAE, the investigator is responsible for the measures to be taken to ensure the safety of the study participants.

The following safety issues qualify for immediate reporting to Guerbet since they may alter the current benefit-risk assessment of an investigational medicinal product, or would be sufficient to consider changes in the study drug administration or in the overall conduct of the study:

- Any post-study serious and/or unexpected adverse event that occurs after the subject has completed the study and that is considered as related to the Investigational Medicinal Product by the investigator (causality not excluded).
- Any new event likely to affect the safety of the subjects and that may be related to the conduct of the study or the development of the study drug such as:
 - A SAE which could be associated with the study procedures and which could modify the conduct of the study
 - A significant hazard such as an unusual failure in efficacy.
 - A new finding from a newly completed animal study.

Severe / Serious: the term "severe" is often used to describe the intensity (severity) of a specific event (within the scale mild, moderate, severe). The event itself, however, may be of relatively minor medical significance. This is not the same as "serious", which is based on subject/event outcome or action criteria.

Also, any suspicion of transmission of an infectious agent via an IMP should be considered as a serious and processed as an SAE.

In addition, any adverse reaction resulting from an occupational exposure (i.e. exposition to IMP of an investigating site staff member) may be directly reported to Guerbet.

In this protocol, the following situations will not be considered as SAE, providing that they are clearly documented as such in the subject's source data:

- Any hospitalization that had been planned before the study and that will take place during the study, provided there is no aggravation of the disease to which it is related.
- Hospitalizations, which are not associated to an adverse event (such as hospitalization for check up).
- Any hospitalization planned for the biopsy specimen collection for histology analysis (biopsy, resection, liver transplantation and any treatment) as part of the standard of care of the HCC

 CONFIDENTIAL	Protocol No. GDX-44-008 Version No.4.0 including amendments 1 and 2 12 December 2017	Page 45 / 64
---	--	--------------

